#### **4.6 Blinding/Unblinding**

Not applicable.

#### **4.7 Treatment Compliance**

Treatment compliance will be monitored by drug accountability as well as the subject's medical record and eCRF.

#### **4.8 Destruction of Study Drug**

For this study, study drugs (those supplied by BMS or sourced by the investigator) such as partially used study drug containers, vials and syringes may be destroyed on site.

Any unused study drugs can only be destroyed after being inspected and reconciled by the responsible Study Monitor unless study drug containers must be immediately destroyed as required for safety, or to meet local regulations (eg, cytotoxics or biologics).

On-site destruction is allowed provided the following minimal standards are met:

- On-site disposal practices must not expose humans to risks from the drug.
- On-site disposal practices and procedures are in agreement with applicable laws and regulations, including any special requirements for controlled or hazardous substances.
- Written procedures for on-site disposal are available and followed. The procedures must be filed with the site's SOPs and a copy provided to BMS upon request.
- Records are maintained that allow for traceability of each container, including the date disposed of, quantity disposed, and identification of the person disposing the containers. The method of disposal, ie, incinerator, licensed sanitary landfill, or licensed waste disposal vendor must be documented.
- Accountability and disposal records are complete, up-to-date, and available for the Monitor to review throughout the clinical trial period.

If conditions for destruction cannot be met the responsible Study Monitor will make arrangements for return of study drug.

It is the investigator's responsibility to arrange for disposal of all empty containers, provided that procedures for proper disposal have been established according to applicable federal, state, local, and institutional guidelines and procedures, and provided that appropriate records of disposal are kept.

#### **4.9 Return of Study Drug**

If study drug will not be destroyed upon completion or termination of the study, all unused and/or partially used study drug that was supplied by BMS must be returned to BMS. The return of study drug will be arranged by the responsible Study Monitor.

It is the investigator's responsibility to arrange for disposal of all empty containers, provided that procedures for proper disposal have been established according to applicable federal, state, local, and institutional guidelines and procedures, and provided that appropriate records of disposal are kept.

Arrangements for the return of study drug will be made by the responsible Study Monitor.

## 5 STUDY ASSESSMENTS AND PROCEDURES

### 5.1 Flow Chart/Time and Events Schedule

Table 5.1-1: Screening Procedural Outline (CA209374)		
Procedure	Screening (28 days prior to dosing unless otherwise specified)	Notes
Eligibility Assessments		
Informed Consent	X	Obtain consent prior to performing any testing for eligibility
IVRS	X	An IVRS will be used to assign subject numbers
Inclusion/Exclusion Criteria	X	
Medical History	X	
Safety Assessments		
Physical measurements (including performance status)	X	Includes height, weight, performance status (Karnofsky); baseline EKG, and a focused physical exam is to be performed at screening.
Vital Signs	X	Temperature, BP, HR, RR. Obtain vital signs at screening and within 48 hours of first dose.
Assessment of Signs and Symptoms	X	After obtaining Informed Consent, assess all signs and symptoms within 14 days of first dose, prior to study treatment initiation.
Concomitant medications	X	Within 14 days of first dose.
Laboratory Tests	X	Labs performed locally within 14 days prior to first dose (unless otherwise specified): CBC with differential, serum chemistry (BUN or serum urea level, serum creatinine, sodium, potassium, calcium, magnesium, phosphate, chloride, bicarbonate, and glucose), liver function tests (AST, ALT, total bilirubin, alkaline phosphatase, albumin, LDH).  The following labs can be performed locally within 28 days prior to first dose: TSH, free T3, free T4, hepatitis B surface antigen (HBV sAg) and Hepatitis C antibody (HCV Ab) or Hepatitis C RNA (HCV RNA).
Pregnancy Test	X	Within 24 hours prior to first dose for WOCBP only (serum or urine at the site).

Table 5.1-1: Screening Procedural Outline (CA209374)		
Procedure	Screening (28 days prior to dosing unless otherwise specified)	Notes
Radiographic Tumor Assessment (Chest, Abdomen, Head)	X	Within 28 days prior to first dose. CT/MRI of brain (with contrast, unless contraindicated) required for all subjects. Additional sites of known or suspected disease (including pelvis) should be imaged at screening.
Archived Tumor Tissue or Recent Tumor Biopsy	X	One formalin-fixed paraffin embedded tumor tissue block, or 15 minimum FFPE unstained slides are to be submitted, if available. Submit a copy of the original pathology report along with the sample. Tissue samples from different biopsy procedures are to be submitted if available with each matching pathology report and biopsy date. Tissue sample from the metastatic tumor can be submitted if the primary tumor tissue is not available.

Table 5.1-2: On-Study Procedural Outline (CA209374)				
Procedure	Each Cycle Day 1	2nd Dose of Cycle	Q 8 wks from Day 1 Cycle 1	Notes
Safety Assessments				
Targeted assessments	X			Cycle 2 and beyond. Assessments within 48 hrs prior to dosing to include: Targeted physical exam, performance status and weight. Oxygen saturation by pulse oximetry at rest and after exertion for patients who complain of dyspnea or other respiratory symptoms
Adverse Events Assessment	Continuously assessed using NCI CTCAE v. 4.0.			
Concomitant Medications	X	X		
Laboratory Tests	X			Cycle 2 and beyond: (within 72 hrs prior to dosing) CBC w/differential, LFTs, BUN or serum urea, creatinine. TSH (reflex to free T3 and free T4 if abnormal result).
		X		LFTS only (within 72 hours prior to dosing)
Pregnancy Test	X			
Efficacy Assessments				
Radiographic Tumor Assessments			X	At Week 8 ( $\pm$ 1 week) and every 8 weeks $\pm$ 1 week thereafter, regardless of dosing schedule for the first 13 months then every 12 weeks $\pm$ 1 week until progression or treatment discontinuation whichever occurs later. Subjects with a history of brain metastasis perform surveillance CT/MRI approximately every 12 weeks, or sooner if clinically indicated.

Table 5.1-2: On-Study Procedural Outline (CA209374)				
Procedure	Each Cycle Day 1	2nd Dose of Cycle	Q 8 wks from Day 1 Cycle 1	Notes
Clinical Drug				
Administer Study Treatment	X	X		All subjects start treatment on C1D1 and continue treatment every 2 weeks for a maximum of 24 months or until confirmed progression, unacceptable toxicity, withdrawal of informed consent or discontinuation of the study by the Sponsor. Treatment for all subjects can continue beyond initial investigator-assessed progression. Drug administration is +/- 2 days but no less than 12 days from previous dose. Study drug infusion start and stop times will be recorded.
Other				
Patient-Reported Outcome Measurements	X			Prior to any study-related procedures: FKSI-19, and EQ-5D
Health Resource Utilization	X			Prior to any study-related procedures

Table 5.1-3: Follow-up Procedural Outline (CA209374)			
Procedure	Follow-up Visit 1 (X01) and Visit 2 (X02).	Follow-up after Visit 2 (X02)	Notes
			Follow up Visit (X01) = 30 days from last dose +/-5 days, or may be on date of discontinuation +/-5 days if the date of discontinuation is more than 35 days after last dose. Follow up Visit 2 (X02) = 100-114 days from last dose.
Vital Signs	X		
Physical measurements	X		Includes performance status (Karnofsky)
Adverse Events Assessment	X	X*	*Beyond 100-114 days from the last dose of study therapy, subjects will be followed for ongoing drug-related AEs until resolved, return to baseline or deemed irreversible, or until lost to follow-up or withdrawal of study consent.
Laboratory Tests	X		CBC with differential, serum chemistry (BUN or serum urea level, serum creatinine, albumin, sodium, potassium, calcium, magnesium, phosphate, chloride, bicarbonate, glucose), liver function (AST, ALT, total bilirubin, alkaline phosphatase, LDH), thyroid function (TSH, reflex to free T3 and free T4 if abnormal result)
Review of concomitant medications	X		
Pregnancy testing	X		Serum or urine
Collection of Survival Information	X	X	Every 3 months until death, lost to follow-up, or withdrawal of study consent for 5 years following start of therapy. May be performed by phone contact or office visit.
Radiographic Tumor Assessment	X	X	For subjects who discontinue study treatment for reasons other than PD, follow up scans (or MRIs when appropriate) should be performed every 8 weeks ( $\pm$ 5 days) for the first 13 months then every 12 weeks $\pm$ 1 week until PD, death, lost to follow-up, or withdrawal of consent. Radiographic assessments should not be delayed until the X01 or X02.

Table 5.1-3: Follow-up Procedural Outline (CA209374)			
Procedure	Follow-up Visit 1 (X01) and Visit 2 (X02).	Follow-up after Visit 2 (X02)	Notes
Patient Reported Outcomes			
FKSI-19 and EQ-5D	X	X	At X01 and X02 and then every 3 months for the first 12 months, then every 6 months thereafter, as permitted by local IRB. Assessments can be conducted by phone or mail.
Healthcare Resource Utilization	X	X	To be collected in alignment with PRO's above (, FKSI-19 and EQ-5D). Assessments can be conducted by phone or mail.

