### **5.3.3 Follow-up and Survival Procedures**

The Follow-Up Phase begins when the decision to discontinue a subject from study therapy is made (no further treatment with study therapy).

- Subjects who discontinue treatment for reasons other than tumor progression will continue to have tumor assessments every 8 weeks ( $\pm 1$  week) for the first 13 months from randomization, and every 12 weeks ( $\pm 1$  week) thereafter until documented tumor progression, death, lost to follow-up, or withdrawal of consent.
- Subjects will be followed for drug-related toxicities until these toxicities resolve, return to baseline or are deemed irreversible. All adverse events will be documented for a minimum of 100 days after last dose.
- After completion of the first two follow-up visits, subjects will be followed every 3 months for survival.

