### **6.2.1 Nonserious Adverse Event Collection and Reporting**

The collection of nonserious AE information should begin at initiation of study drug. Nonserious AE information should also be collected from the start of a placebo lead-in period or other observational period intended to establish a baseline status for the subjects.

Nonserious AEs should be followed to resolution or stabilization, or reported as SAEs if they become serious (see [Section 6.1.1](#)). Follow-up is also required for nonserious AEs that cause interruption or discontinuation of study drug and for those present at the end of study treatment as appropriate. All identified nonserious AEs must be recorded and described on the nonserious AE page of the CRF (paper or electronic).

All nonserious adverse events (not only those deemed to be treatment-related) should be collected continuously during the treatment period and for a minimum of 100 days following the last dose of study treatment.

Completion of supplemental CRFs may be requested for AEs and/or laboratory abnormalities that are reported/identified during the course of the study.

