### **7.6.8 Immune Mediated Adverse Events**

IMAEs are specific events occurring within 100 days of the last dose of study drug (which includes pneumonitis, diarrhea/colitis, hepatitis, nephritis/renal dysfunction, rash, and endocrine abnormalities [adrenal insufficiency, hypothyroidism/thyroiditis, hyperthyroidism, diabetes mellitus, and hypophysitis]), regardless of causality, for which subjects received immunosuppressive medication for treatment of the event. The exception to the immunosuppressive medication criteria for IMAEs is endocrine events (hypothyroidism/thyroiditis, hyperthyroidism, hypophysitis, diabetes mellitus, adrenal insufficiency), which are included regardless of treatment since these events are often managed without immunosuppression.

Unless otherwise specified, analyses will be performed by IMAE category on events where immune modulating medication was initiated. Analyses may also be repeated by categories of endocrine events.

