### **Time-to resolution definition**

In order to derive the time-to resolution, overlapping or contiguous AEs within a specific category will be collapsed into what will be termed “clustered” AEs. For example, if a subject (without pre-treatment AE) experienced an AE from 1st to 5th January, another AE (with different PT but within same category) from 6th to 11th January and same AE from 10th to 12th January, these will be collapsed into one clustered AE from 1st to 12th January. [Table 4](#) is summarizing key derivation steps for each type of clustered AEs.

Time-to resolution of AE (any grade) for a specific category is defined as the longest time from onset to complete resolution or improvement to the grade at baseline among all clustered select AEs in this category experienced by the subject. Events which worsened into grade 5 events (death) or have a resolution date equal to the date of death are considered unresolved. If a clustered AE is considered as unresolved, the resolution date will be censored to the last known date alive. Improvement to the grade at baseline implies that all different adverse events in the clustered adverse event should at least have improved to the corresponding (i.e. with same

preferred term) baseline grade. This measure is defined only for subjects who experienced at least one AE in the specific category.

The time-to resolution of AE (grade 3-5) for a specific category is defined similarly with an onset date corresponding to a grade 3-5 AE.

Time-to resolution of drug-related AE (any grade or grade 3-5) is defined similarly but restricted to drug-related AE.

The time-to resolution of AE (any grade or grade 3-5, drug-related or all) where immune modulating medication was initiated is defined similarly with the additional condition that the subject started an immune modulating medication during the longest AE resolution period.

Time-to resolution for a specific subcategory is defined similarly but restricted to event of this subcategory.

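### After visit X02 the schedule follows only drug-related AEs, while IMAE resolution is analysed whatever the cause and censored at a date that survival contacts keep moving forward

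*Protocol*

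**What the plan says.** **Collection.** Protocol Table 5.1-3 fixes the second follow-up visit: "Follow up Visit 2 (X02) = 100-114 days from last dose". After it, the AE row narrows: "subjects will be followed for ongoing drug-related AEs until resolved, return to baseline or deemed irreversible". Section 5.3.3 repeats the limit, "Subjects will be followed for drug-related toxicities until these toxicities resolve, return to baseline or are deemed irreversible", and sets 100 days after last dose as a minimum for documenting all AEs. The row "Review of concomitant medications" is marked for X01 and X02 and blank afterwards. Survival contact continues: "Every 3 months until death, lost to follow-up, or withdrawal of study consent for 5 years following start of therapy".

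Other sections go further. Section 6.2.1 states "Nonserious AEs should be followed to resolution or stabilization", and Section 6.1.1 asks the same for all SAEs. Neither is limited by causality. Section 5.3.2 wants concomitant medication recorded for the whole study.

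**Analysis.** SAP 7.6.8 counts IMAEs "regardless of causality, for which subjects received immunosuppressive medication for treatment of the event"; endocrine events are exempt from the medication condition. SAP 4.2 makes time to resolution and total duration of immune-modulating medication secondary endpoints. For an unresolved event, SAP Appendix 1 says "the resolution date will be censored to the last known date alive". SAP 7.6.2 and the protocol synopsis use the last contact date instead. SAP 7.6.8.4 reports medication duration by summary statistics within the 100-day window and gives no rule for a course still running. SAP 7.4.3 defines concomitant medication by the same 100 days.

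**The concern.** A Kaplan-Meier estimate of time to resolution treats a subject as observed, and still unresolved, up to the censoring date. That is sound only if a resolution before that date would have been recorded. For an IMAE judged unrelated and open at X02, the table asks nobody to check again, yet each survival contact moves the censoring date on. A resolution in that interval has no scheduled route into the data. The estimated curve then stays too high, the median lengthens and the percentage resolved falls.

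SAP 7.6.8.3 reports resolution separately for each IMAE category, with ranges and percentages resolved. With few subjects per category, one such case can set the upper end of a range.

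Medication duration has a related weakness, and here drug-related IMAEs are exposed too. If a course outlasts X02, no scheduled review captures its stop date, and the SAP does not say how the course is to be counted.

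**Working it through.** The plan gives no figure on this point, so there is none to reproduce.

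**Step 1. The rules side by side**

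| Item | Table 5.1-3 / Section 5.3.3 | Elsewhere in the protocol | SAP |
|---|---|---|---|
| AEs followed after X02 | drug-related only | 6.1.1, 6.2.1: no causality limit | 7.6.8: IMAEs regardless of causality |
| Medication after X02 | no review scheduled (Table 5.1-3) | 5.3.2: recorded throughout | 7.4.3, 7.6.8.4: 100-day window, no rule for ongoing courses |
| Censoring of unresolved events | not covered | synopsis: last contact date | 7.6.2: last contact date; Appendix 1: last known date alive |

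Neither censoring date is tied to an AE assessment.

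**Step 2. Longest unobserved interval**

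Inputs: X02 at 100-114 days after last dose and survival contact to 5 years from start of therapy (Table 5.1-3); treatment for at most 24 months (Section 3.1); 1 month = 30.4375 days and 1 year = 365.25 days (SAP Section 8).

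Interval = 5 × 365.25 − day of last dose − (100 to 114), with 5 × 365.25 = 1826.25 days.

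- Last dose at day 0: 1712 to 1726 days, about 56 to 57 months.
- Last dose at month 12 (365.25 days): 1347 to 1361 days, about 44 to 45 months.
- Last dose at month 24 (730.5 days): 982 to 996 days, about 32 to 33 months.

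Each is a maximum: the subject must stay alive and in contact to year 5.

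**Step 3. How many subjects**

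Protocol 8.1 assumes a 13% rate of grade 3-5 IMAEs, and 0.13 × 150 = 19.5, about 20 subjects. The documents do not give the share judged unrelated or the share open at X02. Assuming 10-30% and 20-50%:

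- Low: 20 × 0.10 × 0.20 = 0.4 subjects.
- High: 20 × 0.30 × 0.50 = 3 subjects.

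SAP 7.6.8.3 also analyses any-grade IMAEs, which this count leaves out.

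**Step 4. Direction and size of the bias**

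An illustrative simulation used 200,000 events per setting. None of its assumptions comes from the documents: exponential resolution; onset uniformly 0-107 days before the last scheduled AE assessment; survival contact continuing a mean of 600 days beyond that, capped at 1,700 days from onset; unrelated events never assessed after X02; related events assessed throughout.

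| True median (days) | Share unrelated | Median, censored at last AE assessment | Median, censored at last date alive |
|---|---|---|---|
| 30 | 20% | 30 | 31 |
| 30 | 40% | 30 | 33 |
| 90 | 20% | 90 | 102 |
| 90 | 40% | 90 | 124 |
| 180 | 20% | 179 | 223 |
| 180 | 40% | 179 | 321 |

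With no unrelated events the two rules agree. With a true median of 90 days, the proportion unresolved at one year is 0.06. Censoring at the last date alive gives 0.18 at a 20% unrelated share and 0.31 at 40%. The onset assumption leans towards a large effect, because an event that starts earlier in treatment is observed for longer before X02.

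**The case against.** The strongest reply is that the schedule is not the whole protocol. Section 5.3.3 gives 100 days as a floor. Sections 6.1.1 and 6.2.1 require follow-up whatever the cause, and Section 5.3.2 requires medication to be recorded throughout. Sections 5.2 and 5.8 add that resource-use data, which include concomitant medications, are collected beyond X02. A site that follows Section 6 would observe these events. This stands: a reader might infer from Table 5.1-3 that data on unrelated IMAEs are certain to be lost after X02, and the documents do not support that. They show a contradiction, under which sites may act differently.

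The reply does not remove the problem. Section 6 lets follow-up end once an event is stable, which is not resolution, although such an event has at least been assessed as unresolved. Resource-use data describe encounters and do not require stop dates for medication given for an IMAE. Whichever text sites follow, the censoring date remains unconnected to AE assessment.

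A reader might also infer that medication duration is censored at the last date alive. It is not: SAP 7.6.8.4 states no censoring rule at all.

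It is also fair to say that the larger shifts in the simulation need a 40% unrelated share, above the 10-30% assumed in the subject count, and that these are descriptive secondary summaries.

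**Conclusion.** The point holds as a contradiction in the protocol combined with a censoring date that is not tied to AE assessment. Where sites follow Table 5.1-3, unrelated IMAEs open at X02 are carried as unresolved through unobserved time, and time to resolution is overestimated. The interval is bounded by about 57 months for a last dose at day 0 and about 33 months for a last dose at month 24. It would be wrong to read the upper figure as typical.

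The number of high-grade cases is probably small: 0.4 to 3 under assumed percentages, and possibly none. In the simulation, a 20% unrelated share moves a true median of 30, 90 or 180 days to 31, 102 or 223. Short-lived events are therefore barely affected and long-lasting ones more so. For medication duration the weakness is an unstated rule plus a risk of missing stop dates, not a demonstrated truncation. The primary incidence endpoint and its 20% and 25% criteria in Protocol 8.1 are untouched. This is a minor point that is cheap to correct.

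**What to change.** 1. **Protocol.** Reconcile Table 5.1-3 and Section 5.3.3 with Sections 5.3.2, 6.1.1 and 6.2.1. State that, for every ongoing IMAE regardless of causality, the outcome and the stop dates of immune-modulating medication given for it are collected at the existing 3-monthly contacts. Re-censoring alone cannot correct the percentage resolved, so this step is needed.
2. **Censoring.** Use one rule in both SAP 7.6.2 and Appendix 1, and align the synopsis. Unresolved IMAEs in living subjects are censored at the last AE assessment. Events documented as irreversible are the exception and stay unresolved to the last known alive date, because censoring them earlier would be informative. Appendix 1's treatment of events ending in death can stay as it is.
3. **Medication.** In SAP 7.4.3 and 7.6.8.4, let medication given for an IMAE count past the 100-day window, and flag courses ongoing at the last review as censored.

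The cost is a protocol wording change, two extra questions for a few subjects at contacts already planned, and short edits to four SAP sections. No visits are added.

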### **5.1.1 Retesting During Screening or Lead-in Period**

Retesting of laboratory parameters and/or other assessments within any single Screening or Lead-in period will be permitted (in addition to any parameters that require a confirmatory value).

Any new result will override the previous result (i.e., the most current result prior to first dose of study drug) and is the value by which study inclusion will be assessed, as it represents the subject's most current, clinical state.

Retesting must be completed in accordance with [Table 5.1-1](#).

